8. HYPOTHESIS AND OBJECTIVES

Malnutrition in GEP NET patients entails greater morbidity and mortality and has been described as frequent. However, the prevalence of malnutrition or risk of malnutrition in patients with GEP NET in our country is unknown and its diagnosis is probably underestimated. Knowledge on this subject is still scarce and this is where the motivation for this observational study has arisen from.

NUTRIGETNE aims to be the first stage to subsequently allow to carry out nutritional intervention studies in NET patients. The study will make an extensive description of the impact of the nutritional status in patients with NET. The results will allow us to advance in the knowledge about different nutritional problems that appear in patients with NET, in the use of screening tools in these patients and in relevant information for future clinical practice guidelines.

There are 3 main hypothesis:

1. Malnutrition and the risk of malnutrition in patients with GEP NET is frequent, but its prevalence in our environment is unknown.
2. The nutritional status may influence the prognosis, survival, quality of life or response to treatments in GEP NET patients.
3. Therapeutic approaches in GEP NET patients could have a direct impact on the nutritional status of these patients and may be a possible benefit on early intervention in the event that this negative impact exists.

8.1. Main Objective

- Describe the prevalence of malnutrition and risk of malnutrition in GEP NET patients in Spain.

8.2. Secondary Objectives

- Describe the nutritional status of NET patients by using clinical malnutrition scores, anthropometry, bioimpedanciometry, and analytical parameters.
- Describe the nutritional status of NET patients according to the type of NET.
- Study the association between the nutritional status and the quality of life of the patients.
- Study the association between the nutritional status and the stage of the disease and tumor grade.
- Study the association between the nutritional status and the treatments received by the patient.

- Study the association between the nutritional status and the hormonal functionality of the tumor.
- Study the association between nutritional status and survival of NET patients.
- Describe specific deficiencies or deficiencies of vitamins or trace elements in these patients and study if there is a correlation of these with the treatments or tumor types.

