9.5. Endpoints

- Demographic characteristics: Age and ECOG at inclusion, sex, complete physical examination (including blood pressure and heart rate), enolic and smoking habits, other cancer history.
- NET diagnosis: date of initial diagnose, age at diagnose.
- NET at baseline: location of primary tumor, histological grade, TNM grade, Ki-67, mitotic index, metastatic locations, functional status of the tumor.
- NET treatment:
 - a. Prior treatments: systemic therapies for NET (type, start and end date, best response, progression date), locoregional therapies (type, start and end date, best response, progression date), surgery (dates, outcome) and radiotherapy (type, dose, start and end date).
 - b. Current treatments (at baseline): systemic therapies for NET (type, start date, best response), locoregional therapies (type, start date, best response) and radiotherapy (type, dose, start date).
 - c. Hospitalizations (at baseline): cause, start and end date.
- Target nutritional history: regular weight, loss of weight (start date, duration), weekly food intake (calculation of mean daily caloric intake, mean protein intake, (animal and vegetal), mean carbohydrates intake (simple or complex), mean fat intake (saturate, monounsaturated, polyunsaturated, n-3 and n-6), and mean fiber intake (soluble and insoluble). The PREDIMED score test will be used (appendix 2). Calculation of caloric-protein nutritional requirements, according to ESPEN guidelines. Need for supplementation, if necessary, type of oral nutritional supplement (ONS) used, volume administered (ml / day), type of administration regimen (continuous or discontinuous). Number of intakes per day and volume of intakes and existence of intolerance related to enteral nutrition (EN): Diarrhea, constipation, bloating, nausea, vomiting, regurgitation, fever, ...).
- Nutritional screening test: NRS test (nutritional risk screening) (appendix 3) and SGA test (subjective global assessment) (appendix 4). The GLIM criteria for diagnosis and stratification of malnutrition will be applied.

- Quality of life (QoL) test: EORTC QLQ-C30 (European Organisation for Research and Treatment of Cancer Quality of Life Questionnaire)(appendix 5) and the NET specific questionnaire (GI.NET21)(appendix 6).
- Anthropometry: height, weight at baseline, BMI, triceps fold, brachial circumference, abdominal circumference, calf circumference.

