Appendix

Malnutrition Universal Screening Tool (MUST) for adults

Can be adapted for special circumstances (e.g. when weight and height cannot be measured or when there are fluid disturbances) using specified alternative measurements including subjective criteria. It also identifies obesity (BMI > 30 kg/m²).

Nutritional Risk Screening (NRS 2002)

Table 1 Initial screening			
		Yes	No
1	Is BMI <20.5?		
2	Has the patient lost weight within the last 3 months?		
3	Has the patient had a reduced dietary intake in the last week?		
4	Is the patient severely ill? (e.g. in intensive therapy)		
Yes: If the answer is 'Yes' to any question, the screening in Table 2 is performed. No: If the answer is 'No' to all questions, the patient is re-screened at weekly intervals. If the patient e.g. is scheduled for a major operation, a preventive nutritional care plan is considered to avoid the associated risk status.			

Table 2 Final screening			
Impaired nutritional status		Severity of disease (≈ increase in requirements)	
Absent Score 0	Normal nutritional status	Absent Score 0	Normal nutritional requirements
Mild Score 1	Wt loss >5% in 3 mths or Food intake below 50-75% of normal requirement in preceding week	Mild Score 1	Hip fracture*, Chronic patients, in particular with acute complications: carthrosis* , COPD* , Chronic hemodialysis, diabetes, oncology
Moderate Score 2	Wt loss >5% in 2 mths or BMI 18.5 – 20.5 + impaired general condition or Food intake 25-60% of normal requirement in preceding week	Moderate Score 2	Major abdominal surgery* Stroke* Severe pneumonia, hematologic malignancy
Severe Score 3	Wt loss >5% in 1 mth (>15% in 3 mths) or BMI <18.5 + impaired general condition or Food intake 0-25% of normal requirement in preceding week in preceding week.	Severe Score 3	Head injury* Bone marrow transplantation* Intensive care patients (APACHE > 10) .
Score:	+	Score:	=Total score
Age	if ≥ 70 years: add 1 to total score above		=age-adjusted total score
Score ≥3: the patient is nutritionally at-risk and a nutritional care plan is initiated Score <3: weekly rescreening of the patient. If the patient e.g. is scheduled for a major operation, a preventive nutritional care plan is considered to avoid the associated risk status.			

NRS-2002 is based on an interpretation of available randomized clinical trials.

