APPENDIX 4.**SUBJECTIVE GLOBAL ASSESSMENT (SGA) TEST**

Anexo 2 299

VALORACIÓN GLOBAL SUBJETIVA GENERADA POR EL PACIENTE

Por favor, conteste al siguiente formulario escribiendo los datos que se le piden o señalando la opción correcta, cuando se le ofrecen varias

Nombre y Apellidos _____	Edad _____ años Fecha / /
PESO actual _____ kg Peso hace 3 meses _____ kg	DIFICULTADES PARA ALIMENTARSE: Sí No Si la respuesta era Sí, señale cual / cuales de los siguientes problemas presenta: falta de apetito ganas de vomitar vómitos estreñimiento diarrea olores desagradables los alimentos no tienen sabor sabores desagradables me siento lleno enseguida dificultad para tragar problemas dentales dolor. ¿Dónde? _____ depresión problemas económicos
ALIMENTACIÓN respecto hace 1 mes: como más como igual como menos Tipo de alimentos: dieta normal pocos sólidos sólo líquidos sólo preparados nutricionales muy poco	
ACTIVIDAD COTIDIANA en el último mes: normal menor de lo habitual sin ganas de nada paso más de la mitad del día en cama o sentado	
Muchas gracias. A partir de aquí, lo completará su Médico	
ENFERMEDADES: _____ _____	EXPLORACIÓN FÍSICA: Pérdida de tejido adiposo: Sí. Grado _____ No Pérdida de masa muscular: Sí. Grado _____ No Edemas y/o ascitis: Sí. Grado _____ No Úlceras por presión: Sí No Fiebre: Sí No
TRATAMIENTO ONCOLÓGICO: _____ _____	
OTROS TRATAMIENTOS: _____ _____	
ALBÚMINA antes de tratamiento oncológico: _____ g/dl	
PREALBÚMINA tras el tratamiento oncológico: _____ mg/dl	

VALORACIÓN GLOBAL, teniendo en cuenta el formulario, señale lo que corresponda a cada dato clínico para realizar la evaluación final:

DATO CLÍNICO	A	B	C
Pérdida de peso	<5%	5-10%	>10%
Alimentación	Normal	deterioro leve-moderado	deterioro grave
Impedimentos para ingesta	NO	leves-moderados	graves
Deterioro de actividad	NO	leve-moderado	grave
Edad	65	>65	>65
Úlceras por presión	NO	NO	SI
Fiebre / corticoides	NO	leve / moderada	elevada
Tto. antineoplásico	bajo riesgo	medio riesgo	alto riesgo
Pérdida adiposa	NO	leve / moderada	elevada
Pérdida muscular	NO	leve / moderada	elevada
Edemas / ascitis	NO	leve / moderados	importantes
Albúmina (previa al tto)	>3,5	3'0-3,5	<3,0
Prealbúmina (tras tto)	>18	15-18	<15

VALORACIÓN GLOBAL,

- A: buen estado nutricional
- B: malnutrición moderada o riesgo de malnutrición
- C: malnutrición grave

**VALORACIÓN GLOBAL SUBJETIVA
GENERADA POR EL PACIENTE (VGS-GP)**

HISTORIAL

Identificación del paciente:

A RELLENAR EXCLUSIVAMENTE POR EL PACIENTE

1. Peso:

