Ya que se trata de una valoración subjetiva, cada aspecto del examen es cuantificado por grado de deficiencia. Déficit musculares impactan más en la puntuación final que déficits de tejido graso. Definición de categorías: 0=sin déficit, 1+=déficit leve, 2+=déficit moderado, 3+=déficit severo. Las puntuaciones en estas categorías no son aditivas, pero son utilizadas para establecer clínicamente el grado de la deficiencia (ej.: presencia o ausencia de fluidos)

Tejido Graso:

Grasa en orbitales parpebrales	0	1+	2+	3+
Pliegue tricipital	0	1+	2+	3+
Acúmulos grasos en la cintura	0	1+	2+	3+
Déficit Graso Global	0	1+	2+	3+

Estatus Hídrico:

Edema de tobillo	0	1+	2+	3+
Edema de sacro	0	1+	2+	3+
Ascitis	0	1+	2+	3+
Estatus Hídrico Global	0	1+	2+	3+

Estatus Muscular:

Músculos temporales	0	1+	2+	3+
Clavículas (pectorales y deltoides)	0	1+	2+	3+
Hombros (deltoides)	0	1+	2+	3+
Músculos interóseos	0	1+	2+	3+
Escápula (latisimus dorsi, trapecio, deltoides)	0	1+	2+	3+
Quadriceps	0	1+	2+	3+
Gastronemios	0	1+	2+	3+
Estatus Muscular Global	0	1+	2+	3+

La evaluación cuantitativa global del estado físico del paciente se determina mediante una valoración global subjetiva de todos los déficits corporales que presente el paciente teniendo en cuenta que las deficiencias musculares pesan más que los déficit del tejido graso y éstos más que el exceso de fluidos.

Sin déficit	= 0 puntos
Déficit leve	= 1 punto
Déficit moderado	= 2 puntos
Déficit severo	= 3 puntos

Puntuación Total Tabla 4 = D

TABLA 5.—Valoración Global Subjetiva del Estado Nutricional del Paciente. Categorías

Categoría	Estado A	Estado B	Estado C
	Bien nutrido	Moderadamente malnutrido o sospechosamente malnutrido	Severamente malnutrido
Peso	Sin pérdida de peso o sin retención hídrica reciente	a. 5% pérdida de peso en el último mes (o 10% en 6 meses) Peso no estabilizado	a. >5% pérdida de peso en 1 mes (o >10% en 6 meses) peso sin estabilizar
Ingesta	Sin déficit o Mejora significativa reciente	Disminución significativa en la ingesta	Déficit severo en la ingesta
Impacto de la Nutrición en los Síntomas	Ninguno o Mejora significativa reciente permitiendo una ingesta adecuada	Existe Impacto de la Nutrición en los Síntomas (Sección 3 de la VGS-GP)	Existe Impacto de la Nutrición en los Síntomas (Sección 3 de la VGS-GP)
Funcionalidad	Sin afectación o Mejora reciente significativa	Deterioro Moderado o Deterioro reciente de la misma	Deterioro severo o Deterioro reciente significativo

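### Appendix 4 holds two SGA forms; if the first supplies the grade, the nutrition-treatment association is partly built in, because that form grades the antineoplastic treatment itself

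*Combined protocol and SAP*

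**What the plan says.** Section 8.2 lists among the secondary objectives "Study the association between the nutritional status and the treatments received by the patient". Section 9.5 names the screening instruments as "NRS test (nutritional risk screening) (appendix 3) and SGA test (subjective global assessment) (appendix 4"), and adds that "The GLIM criteria for diagnosis and stratification of malnutrition will be applied". Anthropometry, bioimpedance and laboratory values are also collected.

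Appendix 4 reproduces two different SGA forms.

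- The first is a one-page form with 13 clinical rows, each marked A, B or C. One row is "Tto. antineoplásico", with low, medium and high risk under A, B and C. Other rows cover fever or corticosteroids and "Prealbúmina (tras tto"). The instruction to the rater is "señale lo que corresponda a cada dato clínico para realizar la evaluación final".
- The second is the scored patient-generated form. Its A/B/C grade comes from Table 5, "Valoración Global Subjetiva del Estado Nutricional del Paciente. Categorías".

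Appendix 3 gives NRS-2002. Its final screening adds a 0 to 3 score headed "Severity of disease (≈ increase in requirements") to the nutritional score, plus one point from age 70.

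Section 9.8 names ordinal regression for quality of life, stage and grade. It names no model for treatment, does not say which instrument stands for nutritional status in that analysis, and mentions treatment type only as a possible subgroup.

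**The concern.** An association study needs an outcome that can be scored without knowing the exposure. On the first SGA form it cannot: the rater is asked how risky the antineoplastic treatment is, and the answer counts towards the grade. Two patients with the same weight history, intake, muscle and laboratory values can then be graded differently because their treatments differ. Covariate adjustment does not repair this, because the overlap lies in the definition of the outcome and not in a third variable.

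At stake is the third hypothesis in section 8, that therapy affects nutritional status. Section 7 cites a German cross-sectional study of 203 patients, using SGA and NRS, in which risk was concentrated in high-grade disease and chemotherapy. A similar pattern here could be taken as replication when part of it came from the form. The influence of the row may also vary by centre: section 9.1 lets a nutritionist, nurse or doctor do the rating, and the form does not say which therapies are low, medium or high risk.

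**Working it through.** The plan gives no figure on this point to reproduce. The check is of the content of the instruments, followed by illustrations of size.

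**1. SGA, first form (Appendix 4).** Of 13 rows, one is the treatment itself. Marking C there can only worsen the overall grade or leave it unchanged. No rule for combining the rows is given.

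**2. SGA, second form (Appendix 4).** Table 5 grades weight, intake, nutrition-related symptoms, function and physical examination. None is a treatment item. Steroids (Table 3) and disease (Table 2, cancer = 1 point, hence the same for every enrolled patient) enter the numerical total and are not rows of Table 5. Stage is recorded, but Table 2 gives it no points.

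**3. NRS-2002 (Appendix 3).** At risk means a total of 3 or more, so the nutritional score needed is max(0, 3 − severity − age point).

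- Severity 1: 3 − 1 = 2 under age 70; 3 − 1 − 1 = 1 from age 70.
- Severity 2: 3 − 2 = 1 under age 70; 3 − 2 − 1 = 0 from age 70.

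Oncology is listed at severity 1 with no distinction by therapy, so the score raises the at-risk rate but does not by itself separate treatments. It separates patients through recent major abdominal surgery (listed at 2), or if raters grade severity differently.

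**4. Size, simple illustration.** Assume no true difference, and that the treatment row moves 0, 5 or 10 of every 100 patients on higher-risk treatment from A to B or C. These shifts are assumptions. For the base rate take 30% (the malnutrition figure in section 9.3, which names no instrument) or 25% (the upper figure for risk by SGA and NRS in section 7).

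- No shift: odds ratio 1.00 at either base.
- Base 30%: (0.35/0.65)/(0.30/0.70) = 1.26; (0.40/0.60)/(0.30/0.70) = 1.56.
- Base 25%: (0.30/0.70)/(0.25/0.75) = 1.29; (0.35/0.65)/(0.25/0.75) = 1.62.

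**5. Size, if rows were summed.** A simulation scored A/B/C as 0/1/2 and made the 12 other rows unrelated to treatment. Assumed inputs were P(B) = 0.20 and P(C) = 0.08 per row, with inter-row latent correlation 0.36. At a cut-off of 6 the malnourished share was 30.7%, 38.0% and 46.6% for low-, medium- and high-risk treatment. The high-to-low odds ratio is (0.466/0.534)/(0.307/0.693) = 1.97. Across cut-offs from 3 to 10 it ran from 1.76 to 3.73. With the treatment row removed it is 1 by construction. The form prescribes no sum, so this shows direction and not expected size.

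**The case against.** The strongest reply is that the circularity is conditional. The second form is also appended, its Table 5 is free of treatment, and a site using it has no direct overlap. This stands, and a reader who infers that the SGA result is circular whatever happens goes further than the documents allow. But the choice is left open, so it is no safeguard.

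Second, the first form calls for a global judgement, and one C among twelve A's need not change the grade. This also stands: it is why no size can be claimed, and why it is too strong to say that a spurious association would certainly be reported.

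Third, a reader might extend the point to the NRS. The documents do not support that for type of therapy, since oncology scores 1 throughout. Appendix 3 does say that a diagnosis need not always fall in the same severity category, so some link through surgery or rater judgement is possible, but none is fixed by the form. Nor is a built-in link to stage or grade shown: no row of the NRS or of the first SGA form scores either.

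Fourth, section 9.8 says results are to be read descriptively only, and section 10.6 cautions about causality between treatments and nutritional status. Neither helps here, because a description is still distorted when the exposure is scored into the outcome.

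Last, treatment risk may properly count when the aim is to flag patients at risk, as in the primary objective. This is fair, and the prevalence analysis is not challenged.

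**Conclusion.** The point holds in conditional form. If the first Appendix 4 form supplies the SGA grade, the association in section 8.2 between nutritional status and treatments received is partly built in, towards worse status with treatment judged higher risk. If Table 5 of the second form is used, there is no direct overlap. The protocol does not say which applies and plans no analysis without the treatment row.

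The size is not derivable. The illustrative odds ratios, 1.00 to about 1.6 under assumed reclassification and 1.76 to 3.73 under an assumed summing rule, are not estimates for this study. For GLIM nothing can be shown either way, because its items are not in the documents. The issue touches one secondary objective and is cheap to remove, so it is a worthwhile improvement and not a threat to the primary result.

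**What to change.** 1. In Appendix 4 and section 9.8, name Table 5 of the second form as the source of the SGA grade for the treatment objective, and do not use the first form's grade as the outcome there.
2. In section 9.8, analyse the treatment association on measures with no treatment item: the Table 5 grade, percent weight loss (from regular and current weight), BMI and phase angle. The ordinal model already named for stage and grade can carry the Table 5 grade.
3. Report the NRS total for this objective with a sensitivity analysis on its impaired-nutritional-status sub-score alone. Set the sub-score to 0 when the initial screen is negative, since the final screening is then not done.
4. Store the NRS sub-scores and the individual SGA row entries in the eCRF as well as totals and grades. A global grade cannot be recomputed afterwards by deleting a row.
5. Leave the prevalence analysis as planned.

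The cost is plan wording and some eCRF fields, with no extra patients or visits. There are two downsides: the second form must be completed for every patient, and the outcome in the treatment analysis may differ slightly from the headline prevalence variable, which the report should state.

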9. RESEARCH METHODS

9.1. Study design

NUTRIGETNE is an observational *cross-sectional, epidemiologic, non-interventional, multicenter* study in which the nutritional status of patients with GEP NET in Spain will be evaluated. It is planned to include 400 GEP NET patients. Patients will be included consecutively when visiting the corresponding health centers for outpatient visits or hospitalization.

The study will use secondary data retrieved from medical records from each patient. The medical records include all the clinical variables defined in order to perform the analysis and it is not necessary to access additional sources. Patients will be asked to provide a signed informed consent as detailed in section 10.3 and fulfill a set of tests and questionnaires in one visit during their participation in the study to assess their nutritional status. Detailed information about the tests and determinations to be performed to the patients during their participation in the study is listed on section 9.3.

The assignment of a patient to a specific therapeutic strategy has been already decided in advance by the usual clinical practice of medicine; the decision to prescribe a specific treatment was clearly dissociated from the decision to include a patient in the study. There will be no specific target treatment or medicine for this study, only epidemiological methods will be used to analyse the data collected.

The study comprises 3 stages with a total duration of 10 to 40 days for the participation of each subject in the study:

- Screening visit, First day (day 0): The initial screening will take place on the first day the patient visits the hospital. The inclusion and exclusion criteria will be reviewed to assess the eligibility of the patient. The implications of the study will be explained to the patient and the informed consent will be signed.
- Visit for assessment of nutritional status (days 0-10): taking a medical history, complete physical examination including anthropometry, bioelectrical impedance (BIA) and dynamometry, as well as laboratory analysis. The evaluation of the nutritional status will be carried out by a registered nutritionist, specialized nurse or specialist doctor (variable depending on the characteristics of the center).
- Data collection (day 10-40): collection of analytical, anthropometric, BIA, dynamometry and clinical results and introduction into the eCRF.

After the end of recruitment and database lock, all data will be subsequently analyzed and presented when applicable through study reports and scientific communications.

9.2. Setting and study population

Approximately 400 adult patients diagnosed with gastroenteropancreatic (GEP) neuroendocrine tumors (NETs) will be selected at 16 hospitals in Spain.

The beginning of patients' documentation with first patient enrolment is planned for 2Q 2021; the planned total duration of inclusion is 12 months (2Q 2022). The last patient observation is planned in 2Q 2022. Subsequently, it is considered a period of data analysis and clearing of 6 months and 12 months more for results interpretation, presentation and / or publication. End of study, including data publication, is planned for December 2023.

